4. IND/IDE: *N/A*
5. Biosafety: *N/A*
6. Stem cell research: *N/A*

## 1. Procedures Involved

1. Study Design: This study is double-blind, within subject, and sham-controlled. The scientific integrity of the trial and the credibility of the data from the trial depend substantially on the trial design. A description of the trial design includes: In a double-blind randomized design, 100 abstinent (approximately 2 weeks abstinent) individuals with alcohol use disorder (AUD) recruited from Lodging Plus Program will receive 10 sessions (2 sessions per day for 5 days) of either (i) active transcranial direct current stimulation (tDCS) to DLPFC or (ii) sham-tDCS. All subjects will perform the reversal learning task during tDCS intervention (active or sham) to prime the engagement of the NAcc-PFC brain circuit that mediates cognitive flexibility (D'Cruz et al., 2011). Rest fMRI and craving measures will be collected before the first and after the last day of tDCS sessions. Follow-up interviews will be scheduled for each month, but may not happen exactly every month, depending on the participant's availability. Follow-ups will be conducted for approximately 8 months after study completion to query relapse status. Dependent variables will be (i) change in NAcc-DLPFC FC between 2 and 3 weeks of abstinence, (ii) change in craving scores between 2 and 3 weeks of abstinence and (iii) monthly queries on relapse status for the next 6 months after intervention completion. Aim 1: To investigate whether NAcc-DLPFC FC can be modulated, we will compare magnitude of change in NAcc-DLPFC FC between active-tDCS and sham-tDCS groups. Aim 2: To determine if DLPFC stimulation has a short-term effect on behavior related to clinical outcome, we will compare change in craving scores (difference in craving scores between 2 and 3 weeks of

abstinence) between active-tDCS and sham-tDCS groups. Aim 3: To correlate neuromodulation intervention with long-term clinical outcome, we will record monthly craving and relapse status ~8 months after intervention completion. We will examine the relationship between change in NAcc-DLPFC FC between 2 and 3 weeks of abstinence and subsequent (i) monthly craving scores and (ii) relapse status. Patients will be asked to complete these scales monthly for ~8 months after intervention completion to examine long-term effects. Patients will be asked to come back for 3 in-person (or remote) visits scheduled approximately 1, 4 and 8 months later, with the actual date of each visit varying depending on participant availability. On a case-by-case basis, follow-ups may be scheduled up to 3 months after each timepoint (1, 4, and 8 month timepoints) depending on participant availability. In these in-person (or remote) visits the participants will complete the same assessments and fill out questionnaires assessing behavior, personality and substance use metrics as in the baseline appointment. At the ~1-month follow-up timepoint, the participant will also complete a third MRI session, which could be on the same day of the assessments and questionnaires or on a different day, depending on participant availability.

2. Study Procedures: Randomization: Participants will be randomly assigned to either active or sham tDCS. Blinding: Participants will not be informed on their assigned protocol. During consent, they will be informed that there is a 50% chance of receiving active tDCS or sham tDCS every day for five consecutive days. Study appointments will be conducted either in-person, or remotely.
3. Participants who consent to the study and meet study criteria as per the screening evaluation will be asked to participate in an 8-day session study, be available for monthly phone follow-up measures after study completion to query relapse status and for 3 in-person (or remote) follow-up visits. At any of the in-person follow-up visits, research staff may test participants for recent alcohol use using a Breathalyzer (will not be administered if assessments are remote). Participants will be informed of alcohol level, but will not be excluded from the study if test shows recent alcohol use. If Breathalyzer shows alcohol level of > 0.08%, participant will be asked to reschedule visit. While the target will be to conduct follow-up phone calls every month, plus in-person/remote assessments at 1, 4 and 8 months

timepoints, the actual date for these follow-up sessions will vary depending on participant availability.

The participants who are referred to our study by the Consortium of Addiction Research (CAR; approved under IRB protocol #STUDY00005170) will be asked if they are interested in participating. Participants will be informed about the study via the “1406M51241 Invite,” which informs them that they need to be available for 8 appointments during their stay at the treatment program. They also need to be available for monthly (depending on subject availability) phone follow-up measures after study completion to query relapse status and for the 3 in-person (or remote) follow-up visits.

**Baseline Interview:** A research staff member will meet the participant either in person or through a virtual video conference to complete the informed consent process with the participant and administer surveys assessing behavior, personality and substance use, and alcohol craving levels. Understanding of informed consent will be assessed with the “Assessment of Informed Consent” form. Participants will also complete a screening questionnaire for contraindications of MRI scanning. Females who could potentially be pregnant will be tested for pregnancy and, if positive, will not be allowed to participate. If testing is refused, participation will not be allowed. Baseline assessments will take about 1.5 hours total.

**MRI #1:** The participant will undergo an MRI scan (3T), which takes about 75 to 80 minutes. MRI involves taking pictures of the participant's brain, from which the properties of certain brain tissues can be measured. While sometimes MRI scans are done for clinical purposes, the scans the participant will receive are being done for research purposes. Since these scans are not designed for clinical or medical reading, the participant's scans will not receive a clinical or medical interpretation. For the scan, the participant will be asked to lie down quietly on a bed, and the bed will slide into the scanner. Once the participant is inside the scanner, it will start to take the pictures. During the scan, the participant will simply lie quietly in the scanner with eyes closed while the scanner takes images of the participant's brain. The MRI scan will be performed at the University of Minnesota's Center for Magnetic Resonance Research. Day 2 assessments will take about 1.5 hours total.

**Interventions Days 1-5:** Will involve reversal learning task training and two

tDCS interventions. We will first explain to the participant what the reversal learning task is, and the participant will perform one trial/practice run.

During the reversal learning task the participant will be presented with four identical stimuli. The participant will be required to choose the stimulus that is in the correct location (correct location is randomly determined and changes across trials). Before and after completion of all tDCS interventions (pre-intervention and post-intervention), the participant will perform the following two tasks:

Before and after completion of all tDCS interventions (pre-intervention and post-intervention), the participant will perform the following two tasks:

1. **Computerized dimensional set shifting task** (available in jspsych <https://expfactory.github.io/experiments/>): this will measure whether changes in cognitive flexibility generalize to a task similar to the task that is practiced (reversal learning task, IRB approved) jspsych <https://expfactory.github.io/experiments/> (additional 7 minutes).

The Computerized Dimensional Set Shift task is a test of rule acquisition and reversal. It involves visual discrimination and attentional set formation maintenance, shifting and flexibility of attention. This test is sensitive to changes in the fronto-striatal areas of the brain and is a computerized analogue of the Wisconsin Card Sorting test.

[figure not shown]
Task Description: In this task, participants must use feedback to work out a rule that determines which stimulus is correct. After a variable number of correct responses, the stimuli and/or rule changes. Initially the task will involve simple stimuli which are made up of just one of the dimensions, i.e. different geometric shape or line. Later on in the task, compound stimuli are used: different types of geometric shapes and different types of lines. The shifts in rule are initially intra-dimensional (i.e. shape remain the only relevant dimension) and then later extra-dimensional (i.e. line become the relevant dimension).

**A**

**2. Risk Task** (Gilmore et al. 2018; Rogers et al. 1999): To evaluate whether there is a generalization effect, the Risk task will be administered before and after the complete course of intervention.

The Risk Task is a computerized behavioral measure of the propensity for risk-taking within a decision-making task, wherein participants must make a choice between high- and low-risk options determined by the ratio of blue or red colored boxes potentially hiding a single token; the higher-risk option being associated with the higher value reward.

**B**

Two typical displays from the decision-making task are shown below, Figures A and B. The subject is told that the computer has hidden a yellow token inside one of the red or blue boxes arrayed at the top of the screen and that he has to decide whether this token is hidden inside a red box or a blue box. However, this decision involves gambling a certain number of points associated with each choice. In the Figure A and B examples, if the subject chooses red, then he/she gains 30 points if the yellow token is indeed hidden inside a red box, but he/she loses 30 points if the token is hidden inside a blue box. On the other hand, if the subject chooses blue, then he/she gains 70 points if the token is hidden inside a blue box, but loses 70 points if it is hidden inside a red box. The subject is told that there is an equal probability that the token would be hidden inside any of the six boxes.

The subject indicates his decision by touching one of the two square response panels, located at the bottom of the display, containing the associated “stake” written in either red or blue ink. Immediately after a selection, one of the boxes opens to reveal the location of the token, accompanied by either a “You win!” or a “You lose!” message written in large yellow font. If the subject chooses the correct color, the stake associated with that color is added to the total points score; if the subject chooses the wrong color, the same stake is subtracted. No monetary significance is attached to the points accumulated by the end of the task. At the start of each sequence, the subject is given 100 points and instructed to make whatever choices thought necessary to increase this score by as much as possible. It is emphasized that these choices might involve either conservative or risk-taking behavior. The ratio of colored boxes (5:1, 4:2, and 3:3) and the balance between the associated rewards

(10 vs 90, 20 vs 80, 30 vs 70, 40 vs 60, and 50 vs 50) vary independently from trial to trial according to a fixed pseudorandom sequence. This sequence ensures that each balance of reward and each ratio of colored boxes co-occurs an equal number of times, with the restriction that on all trials with an unequal ratio of red and blue boxes (i.e., 5:1 or 4:2), the larger reward is always associated with the least likely outcome (i.e., the color with the fewest number of boxes; see Figures A and B), thus capturing the conflict inherent in risk-taking situations.

After the last tDCS day, the participant will be given the same behavior, personality, craving and substance use questionnaires as baseline.

MRI #2: Follow-up MRI scan with the same procedures as baseline will be collected. Total participation time for MRI #2 will be about 3 hours.

#### 4. Optional Procedures

##### **Optional Ecological Momentary Assessment (EMA) self-report surveys.**

We will gather information related to whether or not the participant has experienced: craving, mood states, stressful events, or has used any alcohol or drugs. The purpose of adding optional daily EMA surveys is to obtain a more granular picture of the timing of events leading to a return to alcohol or drug use following treatment. Participants will have the option to fill out the EMA survey both (i) at each visit with research staff while they are in the treatment program if time allows (once for each visit) and (ii) for the 30 days following their residential addiction treatment completion (up to three daily surveys spaced out throughout the day). Surveys will take about five minutes to complete and will be completed via a secure internet enabled REDCap survey. Only participants who will have a cell phone that receives text messages after discharge from the addiction treatment program will be able to opt in the EMA procedure.

*During visits with our research staff while staying in the Lodging Plus treatment program.* EMA surveys (up to one per day) will be completed on a computer via REDCap. REDCap version of the paper survey in ETHOS may appear different because of formatting within REDCap. Study staff will be available at each of these appointments to answer questions participants have about the EMA survey. Participants will be compensated \$1 for each

EMA completed. Participants will only complete the EMA surveys if time allows while in the treatment program.

*After discharge from Lodging Plus*, participants will receive text messages for 30 days with an embedded link to complete a REDCap survey assessing mood, substance use/urges, and use of coping skills. Participants will receive a text message at 9am, 2pm, and 7pm including the embedded link to the REDCap survey. The survey will be open until midnight that day and participants will receive reminders every 1.5 hours or until it is complete. Daily reminders will stop at 8:30pm in the evening (or earlier if completed). Participants will be compensated \$1 for each survey completed. Payment will be given weekly and these payments will be processed on the business day following each 7-day window. At each weekly payment, participants will get a \$5 bonus if they have completed at least 2 EMA assessments per day in the past week.

Text messages will be generated through the REDCap and Twilio integration with all data stored in REDCap's secure server. Data will be entered directly into the REDCap survey and REDCap ensures that SMS transcriptions are not stored in Twilio servers, but are shortly removed after completing for security reasons. REDCap version of the paper survey in ETHOS may appear different because of formatting within REDCap.

During the first week of the EMA procedure, study staff will monitor completion rates and may contact a participant if two days in a row are missed. Participants will be informed that EMA data is not being monitored and will be provided mental health resources at the end of every survey. Once a participant completes a survey, they will not be able to open it again.

**Optional Wearable Device.** To collect objective data about sleep, activity and other physiology information that may affect treatment outcome, we will use a consumer wearable device, the Garmin VivoSmart4 device. This device is worn on the wrist and is equipped with an accelerometer, an optical heart rate monitor, barometric altimeter, ambient light sensor, and a blood oxygenation saturation monitor. The device provides measures on sleep, physical activity, heart rate (every sec), and stress level. If the participant agrees to this optional portion, they will install the Garmin Connect App on their mobile device with a Garmin Connect account and then the **participant authorizes Garmin to transfer data directly to our**

**secured HST-maintained UMN server.** Garmin Connect App will connect with the VivoSmart4 device at least once a day to pull data to the GarminConnect server. Garmin then pushes the data to the UMN server. This will allow us to monitor that data is being received and that the device is being charged. Participants who agree to this optional portion will wear the device after recruitment and during the complete 8-month follow-up period of this study. The participant will be paid \$80 for wearing the device during the 8-month follow-up period. Besides the upfront App installation and authorizing data sharing, there is no additional burden to the participant. All data stored in the HST-maintained UMN server will be secured, will only be accessible to IRB-approved research staff via password, and will be kept for a total of 6 years. At the end of the 8-month follow-up period the participant will have the choice of returning the wearable device or keeping it for personal use. Research staff will no longer access information collected from the wearable device after the 8-month follow-up period is over.

**Optional Genetic Sampling Procedure.** All participants will be given the option to provide one saliva sample for genetic analyses. This sample may be collected at any point during participation of the study. A study staff member will provide the participant with written step-by-step instructions for the collection of a saliva sample using the Oragene DISCOVER saliva self-collection kit (DNA Genotek, Ottawa, ON, Canada, Catalog number OGR-500) and ask the participant to not eat, drink, smoke or chew gum for 30 minutes before giving a saliva sample. The total amount of saliva collected is approximately 2 milliliters (about half a teaspoon) and will take approximately 5 minutes to complete.

Nucleic Acid (DNA) Extraction:

Collected samples will be stored in the laboratory of [name] at the University of Minnesota ([name]). Saliva samples will be processed for DNA using the prepIT extraction kit following the manufacturer's standard protocol (DNA Genotek, Ottawa, ON, Canada, catalog number PT-L2P-5). Extracted DNA will be quantified by the Quant-iT™ PicoGreen™ dsDNA Assay Kit (Invitrogen, Waltham, MA USA, Catalog number P7589) using the Synergy HTX multi-mode plate reader (BioTek Instruments, Winooski, VT, USA).

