## STUDY SUMMARY

Study Title	Effects of Neuromodulation and Cognitive Training on Brain Networks Associated with Relapse in Alcohol Use Disorder
Study Design	Double-blind, within subject, and sham-controlled
Primary Objective	The overall objective of this proposal is to enhance FC between DLPFC and NAcc as a therapeutic intervention to enhance cognitive flexibility.
Secondary Objective(s)	Reduce craving in addiction.
Exploratory Objective(s)	Explore associations between genotype/epigenetic changes and intervention response.
Research Intervention(s)/ Investigational Agents	Transcranial direct current stimulation and magnetic resonance imaging.
IND/IDE # (if applicable)	N/A
Investigational Drug Services # (if applicable)	N/A
Study Population	Individuals with alcohol use disorder
Sample Size (number of participants)	100 consented
Study Duration for Individual Participants	8 months, up to 4-month extension available depending on participant availability for follow-ups

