## 1. Objectives

2. The overarching goal of this project is to expand the traditional expertise in non-invasive neuromodulation at the University of Minnesota towards developing novel paired-neuromodulation approaches using tDCS for new addiction treatments that support long-term abstinence. This study will allow us to investigate whether the pairing of DLPFC stimulation and cognitive flexibility training can enhance FC between DLPFC and NAcc. We have identified higher FC between DLPFC and NAcc in alcoholics that have successfully maintained abstinence for extended periods of time (7 years). This paired-neuromodulation approach can potentially be used as a therapeutic intervention to decrease relapse probability in addiction. The long term goal is to develop new addiction treatments that support long-term abstinence. The overall objective of this proposal is to enhance FC between DLPFC and NAcc as a therapeutic intervention to enhance cognitive flexibility and reduce craving in addiction.
3. Exploratory objectives: To associate genotypes and epigenetic changes with variations in intervention response and clinical outcome.

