3. Existing Literature: Cognitive flexibility, the ability to change maladaptive behavior, depends on DLPFC input to NAcc (Gruber, Hussain, and O'Donnell 2009). DLPFC transmits reward representations to NAcc through glutamatergic projections that guide goal-directed behavior (Ballard and Knutson 2009). If DLPFC fails to activate when required, a common observation in substance use disorder, target neurons in the NAcc core do not receive critical information needed to select the appropriate outcome, causing acquired maladaptive response patterns to persist (e.g. drug consumption) (Gruber, Hussain, and O'Donnell 2009). Higher FC between DLPFC and NAcc may be achieved by stimulating DLPFC while subjects perform a task that requires cognitive flexibility, the reversal learning task. Transcranial direct current stimulation (tDCS) is a non-invasive brain stimulation technique that can modulate brain connectivity. DLPFC stimulation may increase input to NAcc to facilitate proper selection of goal-directed behavior and may also decrease craving in individuals with substance use disorder (Boggio et al. 2008). Genetics and treatment response: A source of treatment response variability could stem from differences between participants in baseline genetic profiles or epigenetic changes over the course of treatment. Genetic polymorphisms, especially in genes important for neuroplasticity, may also mediate neuroplastic changes underlying the effects of tDCS (Chhabra et al., 2016), as has been demonstrated with gene BDNF (Antal et al., 2010; Fritsch et al., 2010). In light of these genetic influences on key tenants of our study - i.e. treatment response in alcohol use disorder and physiological effects of tDCS - we will collect genetic samples from participants to determine whether genetic or epigenetic variations may affect

response to the cognitive training and tDCS intervention. This information may help inform the development of more individually-tailored treatment protocols in the future. As this is a secondary aim, participants will be given the choice in the consent form to opt in or out of the genetic sampling procedure.

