### **3. Study Endpoints/Events/Outcomes**

1. Primary Endpoint/Event/Outcome: In a double-blind randomized design, 100 abstinent (~2 weeks abstinent) individuals with alcohol use disorder (AUD) recruited from Lodging Plus Program will receive 10 sessions (2 sessions per day for 5 days) of either (i) transcranial direct current stimulation (tDCS) to the PFC or (ii) sham-tDCS. All subjects will perform the reversal learning task during tDCS intervention (active or sham) to prime the engagement of the NAcc-PFC brain circuit that mediates cognitive flexibility. Rest fMRI and craving measures will be collected before the first and after the last day of tDCS sessions, and about one month after the last fMRI (timepoint depending on participant availability). Monthly follow-up interviews will be conducted for approximately 8 months after intervention completion to query relapse status. Dependent variables will be (i) change in NAcc-PFC FC between 2,3 weeks of abstinence and one month later, (ii) change in craving scores between 2 and 3 weeks of abstinence and (iii) relapse status ~8 months after study participation. Aim 1: To investigate whether NAcc-PFC FC can be modulated, we will compare magnitude and durability of change in NAcc-PFC FC between active-tDCS and sham-tDCS groups. Aim 2: To determine if PFC stimulation has a short-term effect on behavior related to clinical outcome, we will compare change in craving scores (difference in craving scores between 2 and 3 weeks of abstinence) between active-tDCS and sham-

tDCS groups. Aim 3: To correlate neuromodulation intervention with long-term clinical outcome, we will record craving and relapse status during the ~8 months following treatment discharge. We will examine the relationship between change in NAcc-PFC FC between 2 and 3 weeks of abstinence and subsequent (i) monthly craving scores and (ii) relapse status. Aim 4: Examine relationships between genetic variants, epigenetic changes and treatment outcome (e.g. durability, functional connectivity).

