## Genetic analyses:

DNA extracted from saliva specimens will be standardized to a working concentration of 10-25ng/l prior to analyses. Targeted gene variants will be genotyped using TaqMan SNP Genotyping assays and the Applied Biosystems 7500 Real Time PCR system (Applied Biosystems, Foster City, CA, USA), Restriction Fragment Length Polymorphism (RFLP) performed by fragment analysis on the 3730 Genetic Analyzer (Applied Biosystems), or multiplexed genotyping assays performed on the MassARRAY System (Agena Bioscience) at the University of Minnesota Genomics Core facility (UMGC). Genome-wide scale genotyping will be performed using microarray or sequencing techniques in consultation with the University of Minnesota Genomics Core (UMGC). For methylation detection studies, DNA extracted from saliva specimens will be bisulfite-converted using the EZ DNA Methylation Kit (Zymo Research, Irvine, CA, USA). Bisulfite-modified DNA will be PCR-amplified using primers designed to cover target gene regions for CpG site DNA methylation detection, and sequenced using the Illumina MiSeq system following a standardized protocol at the University of Minnesota Genomics Core facility (UMGC). Genome-wide methylation assessments will be performed using the Infinium MethylationEPIC BeadChip Kit (Illumina) (or comparable alternative) which interrogates over 850,000 methylation sites quantitatively across the genome at single-nucleotide resolution.

**Optional computerized decision-making task.** Participants will be given the option of completing a novel computerized task that measures decision-making in the context of the neuroeconomics of addiction, the Websurf task. The Web-Surf Task provides a rich behavioral economics data space to explore complex variables that capture multiple aspects of reward valuation and decision-making processes (Sweis et al 2018; Abram et al 2016; Abram et al 2019a; Abram et al 2019b). During this task, participants will be asked to make a series of economic choices on a computer for ~ 30 minutes simulating the experience of surfing the web for entertaining video clips. The participant will be paid \$20 for completing this task. The task can be completed at any visit (remote or in-person) while in Lodging Plus, and/or at any in-person follow-up timepoint. This data may be collected at any point (as many as 3 times) during participation of the study. All data collected using this task will be encrypted and stored on box.umn.edu or on an AHC-

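### Exploratory Aim 4 asks about epigenetic changes, but the plan takes one optional saliva sample at an unfixed time, so change cannot be measured and late samples cannot serve as predictors

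*Combined protocol and SAP*

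**What the plan says.** The epigenetic aim appears in three places, each time in terms of change:

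- Study Summary, exploratory objective: "Explore associations between genotype/epigenetic changes and intervention response".
- Section 1, Objectives: "To associate genotypes and epigenetic changes with variations in intervention response and clinical outcome".
- Section 3, Endpoints: "Aim 4: Examine relationships between genetic variants, epigenetic changes and treatment outcome (e.g. durability, functional connectivity").

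The rationale in Section 2 (Existing Literature) attributes variability in response to "differences between participants in baseline genetic profiles or epigenetic changes over the course of treatment". It then gives a broader reason for collecting samples, which is to "determine whether genetic or epigenetic variations may affect" response to the training and tDCS.

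Section 5, Optional Genetic Sampling Procedure, sets the sampling rule: participants have the "option to provide one saliva sample for genetic analyses. This sample may be collected at any point during participation of the study". Under Genetic analyses, the source of the methylation data is stated: "For methylation detection studies, DNA extracted from saliva specimens will be bisulfite-converted". The genome-wide methylation assay is described under the same heading, and no other type of specimen is mentioned. The Data Analysis Plan (Section 16) contains no methylation analysis and no rule about when a sample must have been taken.

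**The concern.** A within-person change needs at least two timed measurements, and the plan provides one. The change question therefore cannot be answered, whatever the uptake of the optional sample.

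The broader question, whether epigenetic variation between people affects response, can be addressed with one sample. Timing then matters in a way it does not for germline genotype. The protocol itself treats methylation as something that may shift during treatment. A sample taken after the intervention may already reflect stimulation, longer abstinence or a return to drinking. Pooling early and late samples would leave the direction of any association unclear, and a result could be reported as a predictor, or as a change, when it is neither.

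**Working it through.** No sample-size or power figure bears on this point, so the check compares the aim, the sampling rule and the outcome schedule.

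**1. Change scores available.** With k samples per person there are k − 1 successive within-person changes. Here k = 1, so 1 − 1 = 0 per person. That is 0 of 100 consented and 0 of the 70 expected with complete data (Section 25). Fewer than these will give saliva, because it is opt-in, but the result is zero at any uptake.

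**2. Whether one could be shorthand for more.** The optional Web-Surf task, also in Section 5, states expressly that it may be done up to three times. The protocol says so when it intends repeats, and no section describes a second saliva sample.

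**3. Permitted sampling visits.**

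- In-program: Baseline 1 + MRI #1 1 + intervention days 5 + MRI #2 1 = 8. This matches Section 5, where participants "need to be available for 8 appointments during their stay at the treatment program".
- Follow-up: 3, at about 1, 4 and 8 months.
- Total: 8 + 3 = 11, which agrees with the payment schedule in Section 12.

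| Position relative to first tDCS | Visits | Share of 11 |
|---|---|---|
| Wholly before (Baseline, MRI #1) | 2 | 18% |
| Before, counting Day 1 before stimulation | 3 | 27% |
| After stimulation starts | 9 (or 8) | 82% (or 73%) |
| Of these, follow-up visits | 3 | 27% |

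The window is about 8 months, extendable by up to 4 (Section 8), so 8 + 4 = 12 months at most.

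**4. Sample time against outcome time.**

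- *FC and craving change between 2 and 3 weeks of abstinence:* a sample taken after the intervention cannot be read as a predictor. One taken during the intervention days may already reflect stimulation.
- *Durability of FC change (third MRI, about 1 month later, with up to 3 months' allowance, so 1 + 3 = 4 months at the latest):* a sample taken up to MRI #2 still precedes this scan; one taken after the scan does not.
- *Relapse over about 8 months:* a sample taken after tDCS but before relapse still precedes it; one taken after relapse does not. Section 2 puts relapse at about 60% within a year of entering treatment, so samples taken after relapse are a realistic possibility.

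**The case against.** The strongest reply is that the longitudinal reading rests on one clause in the Background. The sentence explaining why samples are collected speaks of variation, which one sample can measure, and the aims speak only of associations and relationships. On that view the fault is mostly loose wording in an optional, exploratory aim, and late samples weaken interpretation without defeating an exploratory association. It can be added that the visit percentages weight 11 visits equally when the rule says only any point, that consent is obtained at baseline so early collection is possible for everyone, and that the absence of an analysis in Section 16 applies to all of Aim 4, genotype included.

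Much of this stands as a limit on scope. Between-person methylation remains analysable, the actual timing of samples is unknown, and nothing shows that timing differs by relapse status. It does not remove the problem. All three statements of the aim say changes, and Section 2 contrasts these with baseline profiles. The between-person question in Section 2 is directional, since it asks what affects response, and so needs samples that precede the outcome. Early collection is possible but not required. Exploratory status can excuse low power, but not an aim for which the design collects no usable data.

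**Conclusion.** The concern holds. As written, the plan gives 0 within-person methylation change scores, so the change question cannot be answered. The predictor question can be answered only from samples that precede the outcome concerned, and the rule does not secure this: 2 of 11 scheduled visits (3 counting Day 1 before stimulation) precede tDCS. Those counts describe what is permitted and assume collection at scheduled visits; they are not a forecast of where samples will fall.

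The effect is limited to the epigenetic half of exploratory Aim 4. Genotype analyses and Aims 1 to 3 are untouched. The change should be made, but it does not threaten the main conclusions of the trial.

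**What to change.** **Main change.** In the Optional Genetic Sampling Procedure, collect the single sample before the first tDCS session, at the Baseline Interview or the MRI #1 visit, and record its date. In the Study Summary and Sections 1, 2 and 3, replace epigenetic changes, including the reference in Section 2 to the course of treatment, with pre-intervention methylation as a predictor of response. A sample taken then precedes every outcome, including the durability scan.

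**Samples already taken later.** Use them for genotype only, or analyse methylation separately by collection date relative to tDCS, the third MRI and relapse. State this rule in Section 16.

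**Alternative.** If the sponsor wants to keep the change question, keep the wording, fix the first sample before tDCS, and add a second at a fixed post-intervention visit such as MRI #2.

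**Cost.** The main change needs protocol wording and a fixed visit for a sample that takes about 5 minutes, with no extra assay. Whether the consent form must also change cannot be judged from the pages available. People who give saliva only later would contribute genotype but not methylation to the predictor analysis. Fixed timing helps only those enrolled after the change; this version is dated 10-25-2021 and enrolment was expected to end in Fall 2022. The rewording and the rule for late samples apply to everyone. The second-sample alternative adds one kit, about 5 minutes and one methylation assay per person, and a consent change.
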